Based on preclinical and clinical data, mechanisms underlying the inferior survival in this population point to excess in labile plasma iron (LPI) as the putative mediator(19). This has prompted the use of ICT to modify the negative effect of iron overload in patients with MDS. Although several reports suggest a survival benefit with ICT (27-31), all of them were non-randomized comparisons and were susceptible to a significant selection bias. We know that patients are selected to receive ICT on the basis of an expected survival; otherwise, they would not live long enough to benefit. Therefore, the improved survival in patients treated with ICT could be completely due to a selection bias that is not necessarily overcome by a matched pair

In a multicenter, open-label, single-arm, 3-year phase II trial (US03), the safety and tolerability of deferasirox was evaluated in lower-risk MDS who had received at least 20 units of RBC and had a serum ferritin  $\geq 1,000 \mu\text{g/L}$ (34). Of the 173 patients that underwent ICT with deferasirox, 51 (28%) experienced hematologic improvement, only seven of which received other MDS related therapy. Therefore, ICT appears to improve hematologic parameters in some MDS patients with iron overload. Mean labile plasma iron (LPI) was measured at baseline in 163 patients, among these patients 68 had elevated levels ( $>0.5 \text{ LPI units}$ ). Concentrations of LPI fell within normal limits in all 47 patients who were assessed at week 13 and remained in the normal range through the duration of the trial (Figure 3). Additionally, there was a decline in the median serum ferritin by 23.2% at one year in the patients who completed at least one year of ICT. Therefore, deferasirox was able to reduce the iron burden in iron-overloaded MDS patients.

[figure not shown]

Figure 3: Mean LPI over 12 months in MDS patients with abnormal LPI at baseline.

The annual discontinuation rates of deferasirox were 45%, 43%, and 35% during years 1, 2, and 3 respectively. The safety profile of deferasirox in this setting was reasonable with discontinuation in 43 patients (24.8%) because of adverse events (such as gastrointestinal disturbances) or disease progression and 23 patients (13.2%) because of abnormal laboratory values (such as increased serum creatinine). All 28 deaths that occurred during the study were considered unrelated to deferasirox.

[figure not shown]

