### **2.4 Risks/Benefits**

The most frequently occurring adverse reactions are diarrhea, vomiting, nausea, abdominal pain, skin rashes and increases in serum creatinine. Among patients with MDS, the major observed toxicity was an increase in serum creatinine (37%). The most frequent adverse reactions that led to drug discontinuation were increase in serum creatinine, diarrhea, nausea, rash and vomiting. Death was reported in the first year in 8% of the patients. Auditory and ocular disturbances occurred in <1% of participants. Deferasirox is considered pregnancy Category C by the FDA as animal studies have demonstrated potential embryonal fetal toxicities with decreased offspring viability with renal anomalies. The potential benefits of deferasirox are reduction in total body iron with improvement in organ function (liver and heart). Additional benefits include the potential to improve hematopoiesis and bone marrow function in general.

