### **3.2 Secondary Objectives**

Secondary objectives include a reduction in RBC transfusion requirements, hematologic improvement, change in serum ferritin levels from baseline to the end of the study as measured on a monthly basis and safety and tolerability of deferasirox.

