#### 4.2.2 Secondary Endpoints

1. Change in RBC transfusion requirements.
2. The proportion of patients who achieve granulocyte or platelet hematologic improvement as defined by the modified IWG response criteria(39).
3. Change in serum ferritin levels from baseline to the end of the study as measured on a monthly basis.
4. Safety and tolerability profile as measured by grade 3 and 4 non-hematologic adverse events

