## 7.7 Criteria for Removal/Withdrawal

A patient may be discontinued from protocol-prescribed therapy under the following circumstances:

- Consent withdrawal at the patient's own request or at the request of their legally authorized representative;
- Any event that, in the judgment of the PI or designee, poses an unacceptable safety risk to the patient;
- If, in the PI or designee's opinion, continuation in the study would be detrimental to the patient's well-being;
- Significant deviation from inclusion/exclusion criteria, in the opinion of the PI or designee;
- A positive pregnancy test at any time during the study;
- An intercurrent illness that, in the judgment of the PI or designee, would affect assessments of the clinical status to a significant degree and requires discontinuation of therapy, or
- Completion of the study
- Evidence of disease progression to a higher stage of MDS or AML as defined by WHO criteria

Once the attending physician has met and discussed the decision with the patient and/or family member, the Notice of Withdrawal from a Research Study form (**Appendix H**) should be filled out.

- Once completed, the form should be faxed to FHCRC Research Coordinator at [contact].
- It is the responsibility of the PI or designee to complete the Notice of Withdrawal From a Research Study Form (see **Appendix H**) and fax it to the FHCRC Research Coordinator at [contact].

Study treatment is defined as "any activity involving a patient described in a protocol that is not part of their routine medical care". Patients that withdraw from study treatment will be asked permission to continue to record survival data up to the protocol-described end of the subject follow-up period as it is important to the integrity of the final study analysis.

Patients that are withdrawn from the protocol will not be replaced as this is intent to treat analysis.

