### **8.2 Study-Specific AE Capture**

Please refer to the package insert of deferasirox for a listing of specific expected AEs.

AEs will be reviewed and captured in the source documentation. AEs occurring from enrollment through 30 days after the last administration of the study treatment will be captured in protocol-specific case report forms (**Appendix J**).

The following events are not recorded as AEs in this study:

- Disease progression or relapse.
- Planned medical or surgical procedures in and of themselves, including those that require hospitalization (e.g., surgery, endoscopy, biopsy procedures) are not considered AEs.
- Abnormal laboratory values grade < 3 (CTCAE v4.03).

In accordance with institutional policy, all SAEs which in the opinion of the PI or designee meet all three of the following criteria will be reported to the IRB within 10 calendar days of learning of the problem:

1. unexpected
2. related or possibly related to the research
3. serious or suggests that the research places research participants or others at greater risk of physical or psychological harm than was previously known or recognized

All other SAEs and deaths, not meeting the expedited reporting criteria, will be reported to the IRB as part of the annual continuation review report to the IRB.

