### **12.3 Other Parameters**

The secondary endpoints change in RBC transfusion requirements, change in serum ferritin, and safety and tolerability will be assessed in a continuous fashion during the entire duration of the study. Patients will remain on study for a maximum of one year. Patients will be assessed for AE and SAEs while they remain enrolled into the study. Patients will have an end of study visit day 30 following completion or withdrawal from the study.

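### The tolerability endpoint counts only grade 3-4 non-hematologic adverse events, so stopping or interrupting deferasirox for a lower-grade symptomatic event is recorded but does not enter it

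*Combined protocol and SAP*

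**What the plan says.** Section 3.2 makes tolerability part of a secondary objective: "change in serum ferritin levels from baseline to the end of the study as measured on a monthly basis and safety and tolerability of deferasirox". Section 4.2.2, item 4, gives the only measure: "Safety and tolerability profile as measured by grade 3 and 4 non-hematologic adverse events". Section 12.3 adds timing but no measure: "safety and tolerability will be assessed in a continuous fashion during the entire duration of the study". Section 15.0 adds only that descriptive statistics will be produced.

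Recording is wider than the endpoint. Section 8.2 states: "AEs occurring from enrollment through 30 days after the last administration of the study treatment will be captured in protocol-specific case report forms". The only grade limit there concerns laboratory values, which are not recorded as adverse events below grade 3. Symptomatic events have no grade floor. Section 7.7 documents withdrawals on "the Notice of Withdrawal from a Research Study form" (Appendix H).

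The background describes stopping in some detail. For the cited 3-year phase II trial, Section 2.2 says "The annual discontinuation rates of deferasirox were 45%, 43%, and 35" percent for years 1, 2 and 3. It also reports 43 patients (24.8%) stopping for adverse events or disease progression and 23 (13.2%) for laboratory values. Section 2.4 says: "The most frequent adverse reactions that led to drug discontinuation were increase in serum creatinine, diarrhea, nausea, rash and vomiting".

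**The concern.** Tolerability usually means whether patients can stay on the drug. Item 4 measures severity instead. A patient who gives up because of persistent grade 2 nausea contributes nothing to it, and neither does one whose treatment is interrupted for a grade 2 rash. Permanent discontinuation, interruption and dose reduction appear in no endpoint and no planned analysis.

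This matters more than usual here. Section 2.3 sets a ferritin target below 100 ng/mL, and Section 2.2 says there are few data on chelation in patients with minimal transfusion or ferritin below 1000 ng/mL. Whether such patients can remain on treatment is one of the things the trial could show. Stopping also bears on the primary result. Section 7.7 specifies an intent-to-treat analysis without replacement, and response is judged at 6 months. Without a count of early stops, a low response rate cannot be separated into inactivity and insufficient exposure.

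**Working it through.** **1. What enters the endpoint.** Take three patients who stop the drug:

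- Grade 3 diarrhea: recorded as an adverse event (Section 8.2) and counted in item 4.
- Grade 2 diarrhea: recorded as an adverse event and not counted in item 4.
- Grade 2 creatinine rise: not recorded as an adverse event (laboratory value below grade 3) and not counted in item 4.

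The stop itself is counted in none of the three cases. The second case is the point here. The third shows why laboratory values need their own line in any table of reasons.

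**2. Checking the cited trial's figures (Section 2.2, 173 patients).**

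- Adverse event or progression: 43/173 = 24.9% (stated 24.8%).
- Laboratory value: 23/173 = 13.3% (stated 13.2%).
- Both differ from the stated figure only by truncation. Together: 66/173 = 38.2%.
- The 45% for year 1 cannot be reproduced, because no numerator or denominator is given.

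**3. Is the 45% a tolerability rate?** Assume it applies to all 173 patients: 0.45 × 173 = 77.9, about 78 stops in year 1. Even if all 66 stops above fell in year 1, at least 78 − 66 = 12 had another reason, and the 43 already include progression. So the 45% is all-cause and overstates intolerance. No stop is classified by grade anywhere in the documents.

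**4. Size in this trial (25 patients, Section 15.0).** Expected stops = 25 × rate. The exact (Clopper-Pearson) limits for x of n are the 2.5% point of Beta(x, n − x + 1) and the 97.5% point of Beta(x + 1, n − x).

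- At 24.8%: 25 × 0.248 = 6.2, about 6. For 6/25 = 24% the limits are 9.4% and 45.1%.
- At 45%: 25 × 0.45 = 11.25, about 11. For 11/25 = 44% the limits are 24.4% and 65.1%.

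The share of these stops due to grade 1-2 events is an assumption between 0 and 100%. The number invisible to item 4 for that reason therefore lies between 0 and 6 in the first case and between 0 and 11 in the second. The upper end of the second range is implausible, because the 45% includes stops unrelated to tolerability.

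**5. Which time point.** Sections 7.3 and 7.4 offer non-responders other treatment at 6 months. At the planned response rate of 0.25, and if all 25 reach that visit, 25 × 0.75 = 18.75, so about 19 patients would receive the offer. Stopping after month 6 would then largely reflect non-response.

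**The case against.** Item 4 is a descriptive profile in a 25-patient single-arm study, and grade 3-4 events are a common and legitimate safety measure. Lower-grade symptoms are on the case report form, withdrawals are documented, and a data and safety monitoring board reviews toxicity every six months (Sections 10.0 and 16.0). Nothing prevents the investigators from tabulating stops at the end. All of this stands. It shows that some of the data will exist, but not that the plan commits to using them.

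Several stronger readings are tempting and are not supported:

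- A reader might infer that a patient who stops for a mild event is classed as having tolerated the drug. The protocol contains no such classification; the stop is simply outside the endpoint.
- A reader might attach the 45% to intolerance, or to grade 1-2 symptoms. The protocol gives it without cause or grade.
- A reader might picture item 4 showing no events among 25 patients while 11 stop. That requires every stop to be below grade 3 and sets an adverse event count against all-cause stopping.
- A reader might conclude that comparison with the cited trial would be impossible. Section 8.2 cites case report forms in Appendix J, which are not shown, so a reason-for-stopping field may exist.

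Two further cautions also stand. The cited trial required at least 20 red cell units and ferritin of at least 1,000 µg/L. This one requires ferritin of at least 100 ng/mL and sets no transfusion minimum. And because dosing is adjusted to ferritin at the clinician's discretion (Sections 7.2 and 7.6.4), some interruptions may reflect ferritin response and not intolerance.

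**Conclusion.** The point holds in limited form. The only stated measure of a named secondary objective leaves out discontinuation and interruption, and so misses those caused by lower-grade symptomatic events. The protocol itself lists diarrhea, nausea, rash and vomiting among the most frequent reactions that led to stopping, with no severity threshold.

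The affected number is uncertain. If the cited rates carry over, roughly 6 to 11 of 25 patients would stop, and an unknown part of those stops would be for grade 1-2 events. That range assumes the rates transfer to a population with less iron loading. It also assumes that the 24.8%, for which no time window is given, is usable over one year. The sample size, the decision rule and the primary endpoint are unaffected. This is an inexpensive improvement to a secondary endpoint that should be made, not an error that undermines the trial.

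**What to change.** Extend item 4 in Section 4.2.2 to report, among all treated patients, the number and proportion who permanently discontinue deferasirox, and separately the number and proportion who interrupt it, by 6 and by 12 months, each with an exact 95% confidence interval.

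Tabulate both by reason:

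- adverse event of any grade
- laboratory value
- ferritin response or target reached
- disease progression
- non-response with a move to other treatment at 6 months
- patient choice
- other

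Name the 6-month figure as the main tolerability summary. Keep the grade 3-4 count as the safety measure.

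The cost is one line of protocol text and one table. A case report form field for stops and interruptions with their reason is also needed if Appendix J lacks one. Appendix H cannot supply this, since it shows no field for the reason and does not cover interruptions. The tolerability figure may look less favourable. Dosing and clinical management are not touched.

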## 5.0 SUBJECT SELECTION

### 5.1 Inclusion Criteria

1. Capable of giving written informed consent prior to any study-specific procedures
2. Diagnosis of MDS as defined by the WHO diagnostic criteria (40) (**Appendix A**)
3. Have very low, low or intermediate risk disease by the IPSS-R (8) (**Appendix B**)
4. Baseline serum ferritin level  $\geq 100$  ng/mL
5. Have an ECOG performance status of 0-2 (41) (**Appendix C**)
6. Age  $\geq 18$
- 7.
8. Anemia defined as hemoglobin  $\leq 10.0$  g/dLHave adequate organ function, including:
  - a. Hepatic: Bilirubin  $\leq 1.5$  times upper limits of normal (ULN), alanine transaminase (ALT), and aspartate transaminase (AST)  $\leq 3.5$  times ULN
  - b. Renal: Serum creatinine  $\leq 1.5 \times$  ULN and estimated GFR  $> 40$  mL/min
9. Males and females with reproductive potential must agree to use medically approved contraceptive precautions during the study and for 3 months following the last dose of deferasirox\*
10. Females with childbearing potential\* must have had a negative urine or serum pregnancy test  $\leq 7$  days before the first dose of deferasirox and must also not be breastfeeding
11. Reliable and willing to make themselves available for the duration of the study and are willing to follow study procedures

\*Women of child-bearing potential, defined as all women physiologically capable of becoming pregnant, unless they are using effective methods of contraception during dosing of study treatment.

Effective contraception methods include:

- Placement of an intrauterine device (IUD) or intrauterine system (IUS)
- Barrier methods of contraception: Condom or Occlusive cap (diaphragm or cervical/vault caps) with spermicidal foam/gel/film/cream/ vaginal suppository
- Total abstinence or (when this is in line with the preferred and usual lifestyle of the subject). Periodic abstinence (e.g., calendar, ovulation, symptothermal, post-ovulation methods) and withdrawal are not acceptable methods of contraception
- Female sterilization (have had surgical bilateral oophorectomy with or without hysterectomy) or tubal ligation at least six weeks before taking study treatment. In case of oophorectomy alone, only when the reproductive status of the woman has been confirmed by follow up hormone level assessment
- Male sterilization (at least 6 months prior to screening). For female subjects on the study, the vasectomized male partner should be the sole partner for that subject

Women are considered post-menopausal and not of child bearing potential if they have had 12 months of natural (spontaneous) amenorrhea with an appropriate clinical profile (e.g. age appropriate, history of vasomotor symptoms) or have had surgical bilateral oophorectomy (with or without hysterectomy) or tubal ligation at least six weeks ago. In the case of oophorectomy alone, only when the reproductive status of the woman has been confirmed by follow up hormone level assessment is she considered not of child bearing potential.

Sexually active males must use a condom during intercourse while taking drug and for 28 days after stopping study medication and should not father a child in this period. A condom is required to be used also by vasectomized men in order to prevent delivery of the drug via seminal fluid.

**Please note that deferasirox may reduce the efficacy of hormonal contraception thus it is recommended to use alternative methods of contraception as described above.**

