#### Laboratory Assessments

- CBC with differential
- Creatinine and GFR estimation
- Hepatitis Panel

Screening evaluations include laboratory evaluations as well as a bone marrow aspirate or biopsy. CBC with differential and record of transfusional requirements in the preceding 3 months will be obtained during the baseline screening. Testing for hepatotropic viruses will be performed during the screening phase to include: Hep A antibody, Hep B surface antibody, Hep B surface antigen, Hep B core antibody, Hep C antibody, and Hep C PCR. Baseline ophthalmologic and audiometric examinations will be performed during the screening phase. It is recommended that the screening bone marrow aspirate or biopsy be performed once a patient has been found to be otherwise eligible. The results from the screening bone marrow aspirate or biopsy will be used as the baseline for analyses. Baseline will be defined as the last assessment or procedure conducted prior to the initiation of deferasirox (Day 1). Baseline evaluations must be performed within 30 days of start of deferasirox except the baseline bone marrow biopsy which can have occurred within 30 days of the start of deferasirox and for pregnancy testing in women of childbearing potential which must be performed within 7 days of the start of deferasirox.

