### 12.2 Method and Timing

All patients will be screened for eligibility following consent. Screening must be completed within 30 days of start of therapy. If the time period between screening assessments and start of therapy is greater than 30 days then screening tests must be repeated. The most recent screening labs prior to start of therapy will be considered the

baseline assessment upon which response by the modified IWG criteria will be based. Screening assessments will consist of CBC with differential, ferritin, hepatic and renal function tests and a bone marrow aspirate or biopsy. Women of child bearing potential must have a urine or serum pregnancy test performed within 7 days of start of deferasirox.

Follow up tests will consist of monthly CBC with differential, monthly ferritin levels, and monthly renal and hepatic function tests while the patient remains enrolled in the trial. Bone marrow aspiration or biopsy will be repeated at 3 months and 6 months following the start of deferasirox, and as clinically indicated. If at any point a patient is suspected to have disease progression, a bone marrow biopsy or aspirate may be obtained to document this progression. Physical exams and detailed history will be obtained on a monthly basis to screen for potential toxicities. The primary endpoint of hematologic improvement in the erythroid lineage will be assessed at 6 months following start of deferasirox. The secondary endpoints of hematologic improvement in granulocytes and platelets will also be assessed at 6 months. At the end of 6 months patients who do not respond will be offered the option of alternative treatment options including enrollment into clinical trials if possible.

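### The Section 5.1 footnote defines child-bearing potential in an unfinished sentence that, read as written, exempts fertile women on contraception from the pre-dose pregnancy test and the breastfeeding bar

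*Combined protocol and SAP*

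**What the plan says.** All of the operative wording is in Section 5.1, Inclusion Criteria.

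- **Criterion 9:** males and females with reproductive potential "must agree to use medically approved contraceptive precautions during the study" and for 3 months after the last dose. An asterisk follows the criterion.
- **Criterion 10:** females with childbearing potential, with an asterisk on that term, "must have had a negative urine or serum pregnancy test" no more than 7 days "before the first dose of deferasirox and must also not be breastfeeding".
- **Footnote to the asterisk:** "Women of child-bearing potential, defined as all women physiologically capable of becoming pregnant, unless they are using effective methods of contraception", followed by a reference to the period of dosing. The sentence ends there without a main verb. A list of five effective methods follows: intrauterine device or system, barrier methods, abstinence, female sterilization and male sterilization.
- **Next paragraph of the same section:** "Women are considered post-menopausal and not of child bearing potential if they have had 12 months of natural (spontaneous) amenorrhea" with a fitting clinical profile, or certain surgery at least six weeks earlier. After oophorectomy alone, the status is granted only once hormone follow-up confirms it.

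The test is also stated in Section 7.3 under Laboratory Assessments ("pregnancy testing in women of childbearing potential which must be performed within 7 days of the start of deferasirox"), in Section 12.2 ("Women of child bearing potential must have a urine or serum pregnancy test performed within 7 days of start of deferasirox"), in Table 2, in item 10 of the Appendix E checklist and in the Appendix F calendar. All five use the term without defining it.

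**The concern.** A definition of child-bearing potential should say who can become pregnant. Contraception lowers the chance of pregnancy but does not change that capability. Contraception used during dosing also says nothing about a pregnancy that already exists at the first dose, which is what the pre-dose test is there to find.

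The stake is participant safety. Section 2.3 lists pregnancy as a contraindication to deferasirox, and Section 2.4 cites possible embryonal and fetal toxicity in animals. The pre-dose test is the only pregnancy test scheduled in Table 2 or the calendar. None of the 17 exclusion criteria in Section 5.2 mentions pregnancy or breastfeeding. In the text provided, breastfeeding is barred only by criterion 10 and checklist item 10, and both depend on the same term.

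**Working it through.** The plan gives no figure for this point. The check is a comparison of texts, followed by a rough count of the women concerned.

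**1. What the footnote does as written.** The sentence has no main clause that the exception could qualify, so the exception attaches to the definition. A woman who uses a listed method is then not of child-bearing potential.

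**2. Whom that removes from criterion 10.** Of the five listed methods, only female sterilization changes the woman's own fertility. The other four (intrauterine device or system, barrier, abstinence, sterilized male partner) leave her fertile. Users of these four are the women at issue.

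**3. Interaction with criterion 9.** Every female with reproductive potential must agree to contraception. A woman who complies with a listed method leaves criterion 10 by doing so. The criterion would keep almost no one, which is strong evidence of a drafting error.

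**4. Whether another place corrects it.**

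| Place | What it adds | Does it expressly settle the reading? |
|---|---|---|
| 5.1, women not of child-bearing potential | Menopausal and surgical grounds only; contraception is not among them | No. It gives conditions that suffice and does not say that contraception users remain of child-bearing potential |
| 7.3, Table 2, 12.2, Appendix F | Test limited to women of child-bearing potential | No. Term not defined |
| Appendix E, item 10 | Repeats criterion 10 without asterisk or exception | No. Term not defined |
| Table 2 (extra tests if clinically indicated), 7.7 (discontinuation on a positive test), 9.3 (24-hour reporting) | Safeguards outside the scheduled test | No. None requires a test before the first dose |

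**5. How many women.** Section 14.0 plans 10 females among 25 patients. The protocol gives neither the share who are fertile, *p*, nor the share of those using one of the four methods in step 2, *q*. Both are assumed here: *p* = 2%, 5% or 10%; *q* = half or all. With *r* = *p* × *q*, the expected number is 10*r*, and the chance of at least one is 1 − (1 − *r*)^10.

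| *p* | *q* | *r* | Expected women | P(at least one) |
|---|---|---|---|---|
| 0.02 | 0.5 | 0.01 | 0.10 | 1 − 0.99^10 = 0.096 |
| 0.02 | 1.0 | 0.02 | 0.20 | 1 − 0.98^10 = 0.183 |
| 0.05 | 0.5 | 0.025 | 0.25 | 1 − 0.975^10 = 0.224 |
| 0.05 | 1.0 | 0.05 | 0.50 | 1 − 0.95^10 = 0.401 |
| 0.10 | 0.5 | 0.05 | 0.50 | 1 − 0.95^10 = 0.401 |
| 0.10 | 1.0 | 0.10 | 1.00 | 1 − 0.90^10 = 0.651 |

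The chance of at most two such women is lowest in the last row: 0.9^10 + 10(0.1)(0.9^9) + 45(0.1^2)(0.9^8) = 0.349 + 0.387 + 0.194 = 0.930. These are chances that the ambiguity arises. The chance that a woman goes untested, or is dosed while pregnant, is lower.

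**The case against.** There is a good case that the protocol means to test every fertile woman.

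- The paragraph on women who are not of child-bearing potential gives only menopausal and surgical grounds. It withholds that status even from a woman without ovaries until hormone results confirm it. A text that strict can hardly mean to grant the status to a condom user. It also names oophorectomy and tubal ligation, which are already in the list of methods, so naming them again would be redundant if any listed method were enough.
- The reference to the dosing period suits criterion 9, which concerns contraception on study and is followed by the list of methods. It suits a test done before dosing poorly. The clause may be what is left of a lost main clause, such as a ban on taking part unless contraception is used.
- Under Section 6.0, the checklist must be signed before treatment starts. Its item 10 carries no exception, and an undefined term would normally be read physiologically.
- A reading that nearly voids a mandatory criterion is unlikely to be applied. Staff would probably test these women.

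All of this stands as evidence of intent, and it limits the point to a minor one. It does not remove it. The only definition of who is of child-bearing potential says something else, and the intended rule has to be inferred.

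A reader might go further and infer that the plan deliberately exempts contraception users, or that nothing else in it bears on the question. The documents support neither. The footnote is a fragment, and the surrounding text leans towards testing.

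**Conclusion.** The point holds as a minor safety correction. As written, the footnote takes fertile women using a listed method out of criterion 10 and, together with criterion 9, nearly empties it. The rest of the protocol points to testing all fertile women but does not say so expressly.

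Few women are likely to be affected: 0.1 to 1.0 expected among 10, with a 10% to 65% chance of at least one. Those figures rest wholly on the assumed shares. It would be wrong to infer from them that women will be dosed untested, because they count only how often the wording would leave a woman's status open. The primary endpoint, the sample size and the decision rule are unaffected.

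**What to change.** In Section 5.1:

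- Replace the fragment with a full sentence that stops at the physiological basis, for example: *Women of child-bearing potential are all women who are physiologically able to become pregnant.*
- Keep the existing paragraph as the description of women who are not of child-bearing potential.
- Move the contraception requirement and its list of methods under criterion 9.
- Add to criterion 10 that the pregnancy test and the breastfeeding bar apply whatever contraception is used.

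Table 2, the calendar and the checklist need no change for this, because they would then take their meaning from a clear definition. The cost is a line or two of text and at most one or two urine tests.
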